Lower NTM rate in CF in countries with standard BCG vaccination. We conducted an independent assessment of country-specific BCG vaccination policies per the WHO and NTM infection rates in 2019 as reported in the European CF Society Patient Registry^{19,20}. Low rates of NTM infection are often observed in European countries that universally vaccinate for BCG, whereas higher rates are seen in countries that have ceased their standard BCG vaccination strategies, especially countries in which vaccination was suspended in the 1980s or 1990s. Similar low NTM rates are seen in CF patients in Brazil²¹. These findings support the hypothesis that BCG vaccination may protect against NTM infection in people with CF.

4. Study Procedures

a. Study design, including the sequence and timing of study procedures (distinguish research procedures from those that are part of routine care).

Study design: This is a prospective, single center, non-randomized open-label study.

Study population: We plan to recruit 60 participants with CF from the JH Adult Cystic Fibrosis Center, 60 participants with NCFB from the JH Center for NTM and Non-CF Bronchiectasis, and 60 healthy control participants, gender and aged-matched to the CF arm, from the Johns Hopkins Center for Immunization Research (CIR).

Study location: Study participants will be seen at the Johns Hopkins Center for Immunization Research located at [name].

Study procedures:

Recruitment:

Recruitment for this study will be conducted either in person or remotely. Participants with CF and NCFB who are current patients of the Johns Hopkins Adult Cystic Fibrosis Center or the Johns Hopkins Center for Nontuberculous Mycobacteria and Bronchiectasis or other Johns Hopkins Pulmonary or Infectious Disease subspecialty clinics will be evaluated for study participation and approached for recruitment if eligible. Recruitment of healthy controls will occur through the Johns Hopkins Center for Immunization Research. Healthy controls will be gender and age-matched to within +/-5 years to the CF arm.

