The vaccination site will be examined for each participant to ensure proper healing and evaluated for any signs of adverse reactions. A digital photograph of the vaccination site will be taken for each participant, without any identifying information included in the photograph, and will be uploaded into each participant's file that is a safely stored under Virtual SAFE Desktop.

Laboratory procedures for study samples:

Study visit 1: pre-vaccination blood sampling:

Baseline testing will include formal latent TB test with T-spot IGRA, and Ag85A IGRA. Specialized analysis will include cytokine, flow, and infection assays.

Study visit 2 and 3 blood sampling:

These subsequent blood draws will be analyzed first to confirm BCG uptake. This will be done by analyzing BCG Ag-specific (including Ag85A) cytokine release using multiplex ELISA & RT-PCR as well as BCG Ag-specific T cell activation using flow cytometry with intracellular cytokine staining (ICCS). Serum cytokines will also be measured.

Blood will also be analyzed to determine if BCG vaccination elicits NTM crossreactive immune responses in CF and NCFB by analyzing *Mycobacterium avium* (*Mav*) and *Mycobacterium abscessus* (*Mab*) Ag-specific cytokine release and T-cell activation using multiplex ELISA and RT-PCR as well as flow cytometry with ICCS.

We will then determine if BCG vaccination alters NTM killing activity in PBMCs from CF and NCFB. This will be done by infecting human monocyte-derived macrophages (MDM) with *Mav* and *Mab* followed by washing. Autologous T cells expanded with BCG for 7 d will then be added at a ratio of 10:1 and co-cultured for 72 hrs at which time cells will be detergent-lysed and *Mav* or *Mab* CFU counts determined by plating.

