> We will use PBMCs to assess the PBMCs from CF, NCFB, and HC pre- and postvaccination for three key trained immunity parameters: i. pro-inflammatory cytokine release, ii. macrophage reprogramming, and iii. epigenetic changes. For proinflammatory cytokine release we will measure the following cytokines IFN β , IFN γ , TNF α , IL-1 β , IL-2, IL-4, IL-6, IL-10, and IL-17. For macrophage reprogramming, we will measure the following 5 populations: inflammatory macrophages, TNF α expressing M1 macrophages, IL6 expressing M1 macrophages, M2 macrophages, and IL-10 expressing M2 macrophages. For the epigenetic changes we will assess the activation mark H3K4Me3 and the repression mark H3K9Me3 in the TNF α and IL6 promoter regions by ChIP assay. We will compare the relative responsiveness of cells from each group (CF, NCFB, and HC) over time from pre-vaccination and the two post-vaccination time points. We will also compare the relative responsiveness of cells from CF and NCFB subjects to those from HCs to determine if there are measurable immune response deficiencies in CF and NCFB patients.

b. If your study involves data/biospecimens from participants enrolled under other research studies with a written consent or under a waiver of consent, please list the IRB application numbers for those studies. Please note: Certificate of Confidentiality (CoC) protections applied to the data in source studies funded by NIH or CDC will extend to this new study if the funding was active in 2016. If this situation applies, Section 36, question 4 in the application will need to be answered "Yes" and "Hopkins Faculty" should be selected in question 7. No other documents are required.

N/A

c. Study duration and number of study visits required of research participants.

Study duration is 6 months. Each participant will have 4 study visits including the Study day 0 visit, study day 30 (+/- 5 days), study day 90 (+/- 14 days), and study day 180 (+/- 45 days), not including screening.

d. Blinding, including justification for blinding or not blinding the trial, if applicable.

This is a pilot study designed to test the efficacy of BCG vaccination for trained immunity against NTM infection in both CF and NCFB individuals. No blinding will be conducted. If the results from this present study are favorable, a larger, blinded, placebo-controlled trial that was powered for efficacy could be designed for either of these two infections.

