e. Justification of why participants will not receive routine care or will have current therapy stopped.

N/A. All CF and NCFB participants will continue to receive routine standard care for bronchiectasis without any interruptions.

f. Justification for inclusion of a placebo or non-treatment group.

All participants will receive the intradermal BCG vaccination. There is no placebo or nontreatment group in this study. Following the results of this study, a larger, blinded, placebocontrolled trial may be designed. g. Definition of treatment failure or participant removal criteria.

The goal of this study is not to achieve efficacy in prevention of infections, but rather to assess biomarkers of immune protection that are altered by BCG vaccination of vulnerable populations. Study samples will not be analyzed in real time.

Given these factors, we do not have specific criteria for participant removal. If there are unforeseen circumstances during which a participant will not be able to present for study visits 2 and 3 (research phlebotomy visits), these will be evaluated on a case by case basis by the PI.

h. Description of what happens to participants receiving therapy when study ends or if a participant's participation in the study ends prematurely.

This is a single vaccine design and there is no further booster vaccine planned. Participants will continue to receive standard of care for their medical conditions during and after study completion.

5. Inclusion/Exclusion Criteria

• Inclusion criteria (CF/NCFB arms):

- Confirmed diagnosis of either CF or NCFB
- Adult male and non pregnant females ages 18-65 (inclusive)
- \circ FEV1 \geq 40%
- Willingness to participate in the study after all aspects of the protocol have been explained and written informed consent obtained.
- o Available for the study duration, including all planned follow-up visits

• Inclusion criteria (healthy controls):

- Adult male and non pregnant females ages 18-65 (inclusive)
- Negative HIV enzyme-linked immunosorbent assay (ELISA), rapid antibody test and/or confirmatory test, if necessary, at screening
- Willingness to participate in the study after all aspects of the protocol have been explained and written informed obtained
- Available for the study duration, including all planned follow-up visits

• Exclusion criteria (all arms):

- Current or prior history of active or latent TB (per report, not formally tested) or NTM infection
- Prior BCG vaccination

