c. Justification and safety information if non-FDA approved drugs without an IND will be administered.

See above. We have received an IND exemption from the FDA for the use of BCG in this study (see Supplemental study documents).

7. Study Statistics

- a. Primary outcome variable.
 - BCG Ag-specific cytokine release
- b. Secondary outcome variables.
 - NTM cross protectivity
 - Development of lung infections among the CF/NCFB arms during the 6-month period
 - Markers of trained immunity
- c. Statistical plan including sample size justification and interim data analysis.

Sample Size Calculations: The primary hypothesis tests are based upon enrollment of 60 individuals within each study arm while assuming a conservative attrition and dropout rate of 10% in each study group. Due to the pilot nature of this project, participants that drop out of the study will not be replaced. Power calculations were based upon testing a mean difference in slopes between groups assuming a within-person correlation of observations of 0.1 and have assumed that baseline response will not differ between groups; preliminary data for standard deviation of markers was obtained from Abate et al. We will have 80% power to detect changes in the mean difference in slopes ranging from approximately 11% (TNF α) to 65% (IL17) for markers of BCG-stimulated immune response, NTM-induced cytokine, and NTM killing activity between the CF and control groups and between NCFB and control groups at each time point at a significance level of 0.05. Given the heterogenous responses in individuals, we consider a mean difference in slopes of 40%, indicative of an immune response deficiency, between groups to be a clinically meaningful difference.

For detecting differences in TI, we will have 80% power to detect mean differences ranging from approximately 10-70% of TI at each time point between groups at a significance level of 0.05 assuming the same conditions as above, with the exception that the time variable will be the pre/post-stimulus condition. We will repeat these analyses for each time point. We have based power calculations using Cohen's f^2 (multiple correlation/1- multiple correlation) due to the lack of available data in these populations to estimate mean differences.

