The data are being recorded on an encrypted laptop and SAFE Desktop. All files will be password protected. Only specified study team members will have access to the data. The data set will not include any sensitive information. All blood samples will be deidentified and will not be traceable back to participant.

e. Financial risks to the participants. N/A

9. Benefits

- a. Description of the probable benefits for the participant and for society.
 - Individual benefits: The individual may experience positive emotions from contributing to the development of patient-centered interventions by being able to share their experiences. They may also benefit from the protective nature of the BCG vaccine.
 - Societal benefits: This study will provide formative information regarding the efficacy of the BCG vaccine to provide immunity towards NTM infections. These data will inform future larger studies designed to study regarding the efficacy of the BCG vaccine against NTM infections in the CF and NCFB populations.

10. Payment and Remuneration

- a. Detail compensation for participants including possible total compensation, proposed bonus, and any proposed reductions or penalties for not completing the protocol.
 - Healthy controls will be compensated \$80 for completion of the screening visit if they are found to be eligible and enrolled in the study.
 - Study participants from all arms will receive \$200 for the initial visit where they will undergo a blood draw and be administered the BCG vaccine. Participants will then receive \$80 for each subsequent study blood draw. Total compensation for participation in this study will be \$360 (excluding compensation for screening of healthy controls).

11. Costs

- a. Detail costs of study procedure(s) or drug (s) or substance(s) to participants and identify who will pay for them.
 - There will be no costs directed towards the participants.

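### The plan provides no masking of laboratory readers to arm or visit; flow gating and colony counts are the readouts most exposed, and a sample code would close the gap cheaply

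*Combined protocol and SAP*

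**What the plan says.** Section 4a (Study design): "This is a prospective, single center, non-randomized open-label study". Section 4f: "There is no placebo or nontreatment group in this study". The comparisons are therefore between disease groups and between visits, not between treatments.

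Section 4d (Blinding): "No blinding will be conducted". The paragraph contrasts this pilot with a possible later blinded, placebo-controlled trial. It makes no separate statement about laboratory staff.

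Section 4a (Laboratory procedures for study samples) describes multiplex ELISA and RT-PCR for cytokine release, flow cytometry with intracellular cytokine staining for T cell activation, five macrophage populations, and a killing assay with "CFU counts determined by plating". Section 7a names the primary outcome as "BCG Ag-specific cytokine release". Section 7b adds NTM cross-protection, lung infections in the two patient arms, and trained-immunity markers.

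Section 8d (Legal risks): "All blood samples will be deidentified and will not be traceable back to participant". Section 4g: "Study samples will not be analyzed in real time".

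**The concern.** Open-label vaccination explains why participants and clinic staff know what was given and to whom. It does not explain why a reader at the flow cytometer or the culture plate should know whether a sample comes from a patient or a control, or from before or after vaccination.

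The plan also states the results it looks for. The abstract expects vaccination to raise markers of protection, and section 4a compares patients with controls to find deficient responses. A reader who knows arm and visit could lean towards either when setting a gate, judging a colony count, or deciding on a repeat or exclusion.

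Batching raises a related risk. Controls come through a different centre from the patients and are matched to the CF arm (section 4a, Recruitment). If samples are run in order of arrival, assay run could line up with arm or visit, and the plan does not say how runs are composed.

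At stake are the between-group comparisons and the within-group changes from baseline, on which nearly all of the study's conclusions rest.

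**Working it through.** **1. Is there a masking provision anywhere?**

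- Section 4d has no exception for laboratory readers.
- Section 8d concerns confidentiality. Removing identity does not by itself remove arm or visit from a label, and the section does not say that it does.
- The section 7c model needs each result linked to a subject, a group and a visit. Some link code must therefore exist, and the statement in section 8d that samples cannot be traced back needs reconciling with that.
- Section 4g says samples are not read in real time, and the only interim look in section 7c is for safety. Nothing requires the code to be open while assays are read.

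**2. Which readouts are exposed?** Flow gating, macrophage populations and colony counts involve reader judgement. ELISA and RT-PCR readouts usually leave less room for it; this is an assumption, because the documents do not describe how they are read. Their exposure is mainly through repeat, exclusion and batch decisions. Lung infection is not a laboratory reading.

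**3. Which shifts bias which estimate?** In the section 7c model, b1 is time, b2 is group and b3 is group by time. Let d be a reading shift on the analysis scale.

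| Shift | Patients before | Patients after | Controls before | Controls after | Difference in change (b3) | What it biases |
|---|---|---|---|---|---|---|
| Constant in one arm | d | d | 0 | 0 | (d − d) − (0 − 0) = 0 | b2 and single-visit group comparisons |
| After vaccination, all arms | 0 | d | 0 | d | (d − 0) − (d − 0) = 0 | b1 and within-group change |
| One arm, after vaccination only | 0 | d | 0 | 0 | (d − 0) − (0 − 0) = d | b3 |

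Only the third kind moves b3.

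**4. How large could the effect on b3 be?** The plan's power figures are 80% power at a significance level of 0.05 for differences in slopes of about 11% (TNF alpha) to 65% (IL17), with 60 per arm and 10% dropout. They cannot be reproduced, because the marker means and standard deviations are not in the documents. Taken as given, with a two-sided test assumed:

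- SE = detectable difference / (1.960 + 0.842) = detectable difference / 2.80
- False-positive rate = P(|Z + shift/SE| > 1.96), with no true difference and the whole shift an arm-by-visit effect

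| Detectable difference | SE | Rate at 5% shift | Rate at 10% shift |
|---|---|---|---|
| 11% (TNF alpha) | 11/2.80 = 3.9% | 24.7% | 72.1% |
| 40% (difference the plan calls clinically meaningful) | 40/2.80 = 14.3% | about 6% | about 11% |
| 65% (IL17) | 65/2.80 = 23.2% | 5.5% | 7.2% |

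The 5% and 10% shifts are assumptions.

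**5. A version that does not use the percentages.** With 60 × 0.9 = 54 evaluable per arm and the plan's within-person correlation of 0.1:

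- SD of change = √(2 × (1 − 0.1)) = 1.342 marker SD
- SE of the difference in change = 1.342 × √(2/54) = 0.258 SD

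An assumed arm-by-visit shift of 0.1, 0.2, 0.3 or 0.5 SD gives a false-positive rate of 6.7%, 12.1%, 21.3% or 49.1% for one marker.

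**The case against.** The strongest reply has four parts.

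- **Section 4d answers a form question about blinding the trial.** A reader might infer that the plan has decided laboratory staff will know arm and visit. The documents do not support that. They are silent on laboratory masking, and de-identified labels may hide some of this information. What stands is that no provision exists.
- **The model already handles much of this.** A reader might infer that any expectation-driven reading biases b3. It does not: a constant arm shift goes into b2, and a common post-vaccination shift goes into b1. Those shifts matter for single-visit group comparisons and for within-group change, but not for the plan's parameter of interest.
- **The large percentages come from the most precise marker.** A reader might take 25% or 72% as the expected error rate, or apply it to every outcome. Neither is supported. The 11% belongs to TNF alpha, and section 7c gives no separate detectable difference for flow gating or colony counts, so no rate can be derived for the readouts where judgement matters most. At the 40% that the plan calls clinically meaningful, the rates are about 6% and 11%, and a shift of 5% or 10% could not by itself produce a 40% difference.
- **Batching all visits together may not be possible.** Section 4a says blood is processed and stored at visits 2 and 3, but not at visit 1, and it does not describe cell preservation. This limits the batching advice. It does not affect coded labels, which work for fresh samples too.

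**Conclusion.** The concern holds as an omission. The plan rules out blinding in general terms and makes no provision for masking laboratory readers, although its conclusions rest largely on laboratory comparisons across groups and visits. The exposure is greatest for flow gating, macrophage populations and colony counts, and probably smaller for the primary cytokine outcome.

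The size is unknown. If an arm-by-visit shift of 5% or 10% did occur, the false-positive rate for one marker could rise from 5% to anything between about 6% and 72%, depending on the shift and on how precise the marker is. This rests on the plan's stated detectable differences, a two-sided test, no true difference, and a shift that is wholly an arm-by-visit effect. It shows what could happen and does not estimate what will. The change is a cheap improvement worth making; its absence does not invalidate the design.

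**What to change.** Replace the blinding sentence in section 4d with text such as:

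> Participants and clinic staff are not blinded. Laboratory staff receive samples under a random code that hides arm and visit; the code list is held by existing study staff outside the laboratory until the marker data are locked. The three arms are mixed within assay runs and, where samples are stored, all visits of a participant are run in the same batch.

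Align section 8d with this, so that it says samples are coded and linkable through the held list.

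The cost is administering the code list and planning the assay runs; participants undergo no extra procedure. Assays on fresh blood can be coded but not batched across visits, so the plan should say which assays use stored samples and whether visit 1 samples are stored.
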